39 Michigan Health System (UMHS) in the past year (from 11/01/17 until 11/01/18; data obtained using
40 Datadirect for cohort discovery results; FPIES ICD10 K52.2). The latter number of encounters only
41 comprises newly diagnosed patients.
42

43 In this study, FPIES patients will be recruited from the UMHS patient cohort. From 11/01/17 – 11/01/18, this
44 cohort comprised 223 newly diagnosed patients at UMHS. Two sub-groups will be identified as follows: *i)*
45 children exhibiting FPIES reactions to 2-3 foods, *ii)* children exhibiting FPIES reactions to 4 or more foods.
46 The reason for separating patients into these two groups is due the existence of two separate groups [one
47 with 2-3 food triggers, and another with more than 4 food triggers] as previously described by the UMHS
48 Allergists who care for FPIES patients (Volertas S., Hudson E., McMorris G., and [name]. *Annals of*
49 *Allergy, Asthma & Immunology* 121:S119 2018).

50
51 The plan is to enroll up to 20 patients with FPIES: up to 10 exhibiting reactions to 2-3 foods, and up to 10
52 exhibiting FPIES reactions to 4 or more foods. Recruitment will take place at the University of Michigan
53 Allergy Clinics, and University of Michigan Pediatric outpatient clinics.
54

55 **Hypotheses:**

- 56 1. Our blood test that we developed will distinguish safe from trigger foods for FPIES patients.
57 2. The mechanism of FPIES involves innate immunity and the identified heatmap pattern for trigger foods
58 will remain after foods are tolerated.

59 **Specific aims:**

- 60 1. Assess the assay's precision by its predictive accuracy in distinguishing safe foods from trigger foods.
61 2. Evaluate the reliability of the test when using a panel of standardized, frozen foods vs freshly prepared
62 foods
63 3. Demonstrate persistence of the immune reaction to trigger foods by comparing results of the test after
64 trigger foods are tolerated to the initial results

65 **Exploratory aim:**

- 66 1. Gain further insight into the pathophysiology of FPIES through single cell RNASeq

67 **Statistical Design:** A random-effects logit model will be used to model the binary outcome (safe or trigger
68 food) as a function of the 9 biomarker measurements in the assay. The random effect in the logit model will
69 take into consideration of the correlated data measured within the same subject. A cluster Receiver

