70 operating characteristic (ROC) curve analysis will be used to assess the precision of the assay. Specifically,
71 we will compute the area under the cluster ROC curve (AUC), along with a 95% confidence interval (CI).
72 The assay is predictive if the lower limit of the 95% CI is above 0.5, which is the null value indicating no
73 predictive ability.

74 **Brief description of the proposed study**

75 FPIES is a severe food allergy to a wide variety of foods in babies and toddlers. Usually, the symptoms
76 resolve between the ages of 3 to 5 years old. However, the children are at risk of failing to thrive, and
77 requiring a nasogastric tube or TPN. The objective of the study is to validate a newly developed blood assay
78 that will rapidly predict safe (non-trigger) foods for the affected children. In our preliminary data (Case Study
79 HUM00155216), the blood assay safely predicted more than 10 consecutive safe foods without triggering
80 an allergic response. Prior to the assay, allergic reactions and ER visits were repeatedly occurring.

81 **Subject Recruitment:** Subjects will be recruited through the University of Michigan Allergy Clinics, and
82 University of Michigan Pediatric outpatient clinics:

- 83 1. Patients may be referred by the clinician caring for the patient.
- 84 2. Pre-screening by reviewing FPIES visits in the past 2 years will be performed. Data Direct, EMERSE
85 and billing codes may be used to identify potential subjects. The patient's primary allergist or
86 pediatrician will be informed about study team's contact with the identified patients.
 - 87 o Patients will then be contacted by email and/or telephone by the clinical members of the
88 study team to explain the study and determine whether they are interested in participating.
89 Opt out information will be provided in the email and by phone contact.
- 90 3. Patients may self-refer:
 - 91 o The study will be listed in UMHealthResearch.org
 - 92 o Flyers describing the study, with study team contact information, will be posted in the
93 participating clinics.

94 **Inclusion Criteria:**

- 95 1. Patients aged 1 month – 7 years old with a physician diagnosis of FPIES:
 - 96 a. Group 1: Documented reactions to 2-3 trigger foods with recurrent delayed vomiting.
 - 97 b. Group 2: Documented reactions to 4 or more trigger foods with recurrent delayed vomiting.

98 **Exclusion Criteria:**

- 99 1. Patients without a physician diagnosis of FPIES.

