- 100 2. Patients who are currently on medications that suppress the immune system.

- 109 3. Patients who do not have at least 2 trigger foods identified.
110 4. Patients who have a history of an organic GI disease (e.g., inflammatory bowel disease, celiac
111 disease, biliary disorders, bowel resection), cardiac, pulmonary, neurologic, renal, endocrine, or
112 gynecological pathology
113 5. Lack of parental or guardian informed consent.

114
115 Study Design

- 118 1. Potential participants will be contacted by email and / or telephone after pre-screening of physician-
119 diagnosed FPIES patients who have visited the UM allergy clinics within the past three years, or who
120 are currently in contact with the UM allergy clinic nutritionist. An option for the patients to opt out will
121 be provided. The patient's primary allergist or pediatrician will be informed about study team's
122 contact with the identified patients. Patients may be referred by their primary allergist during a clinic
123 visit.
124 2. If a parent/guardian expresses interest in the study, they will be sent/given a copy of the informed
125 consent to review.
126 3. An appointment will be scheduled with a study team member at the UM allergy clinics.
127 4. The protocol will be discussed face-to-face with parent/guardian with an opportunity to ask questions
128 and review the informed consent document. After written informed consent is signed by one
129 parent/guardian, study procedures can begin. Parent/guardian will be given a copy of the signed
130 informed consent and it will be imaged into the chart.
131 5. Parent/Guardian will be asked to fill out Questionnaire One at the time of entry into the study.
132 6. Parent/Guardian will be instructed regarding scheduling the blood draw for analysis:
133 a. Only known "safe foods" (foods that do not induce repetitive vomiting) are to be consumed
134 for one week before blood draw.
135 b. Blood draw will be performed at the MLabs Blood Draw Stations at Michigan Medicine
136 outpatient clinics.
137 7. Patient will have 6 ml of blood drawn for analysis:
138 a. 5.5 ml of blood for testing of potential food reactions
139 b. 0.5 ml of blood for RNA/DNA analysis, which will be stored.
140 8. After blood draw, diet will be managed per the primary clinician and nutritionist.
141 a. Parents will be given Questionnaire Two to fill out detailed information about all foods
142 introduced until the results of the assay are received.

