143 b. During that time, food introduction will continue as directed by primary allergist and/or
144 nutritionist
145 9. Blood will be analyzed by the PI in a research lab at the University of Michigan to determine
146 differences in the PI's assay between potentially tolerated and not tolerated foods (see description of
147 laboratory test lines 216-232)
148 10. After identification of potentially "safe foods" to be introduced in the future, the information will be
149 given to the clinical study team and child's clinician, who will contact parents by phone or email
150 (parental preference).
151 a. Parents will be asked to detail current nutritional status, including foods tolerated or not
152 tolerated since the initial blood draw. Results will be recorded by the study team and the
153 parents will be asked to return Questionnaire Two.
154 b. After discussion within the clinical team (including clinical research team and child's
155 clinicians), parents will be instructed to introduce new foods identified as potentially safe into
156 the diet, one at a time for seven days.
157 c. Results of these trials will be recorded on Questionnaire Three and returned to the study
158 team 3 month intervals.

159 11. A second blood draw will be performed, at least 2 weeks after the initial blood draw. 6 cc will be
160 drawn:

- 161 a. To explore the consistency of a standard panel of foods vs individually prepared foods
- 162 b. To perform additional analyses including single cell RNASeq (scRNA-seq) on WBCs
- 163 following treatment with foods.

164 12. Subjects will be followed at 3 month intervals with review of tolerated foods, number and types of
165 known triggers assessed. When a subject is tolerating two or more triggers foods for 3 or more
166 months:

- 167 a. Questionnaire Four will be given to fill out and return
- 168 b. Subject will have 6 mL drawn for analysis
 - 169 i. 5.5 mL to rerun the initial assays
 - 170 ii. 0.5 mL for RNASeq on WBCs following treatment with foods.

171 Study Grid

	Baseline visit - Day 0	Lab Day 0- 14	Lab >2 weeks after initial blood draw	At home 1-3 months	3 up to 36 months	At home every 3 months up to 36 months	> 2 trigger foods tolerated
Consent	X						
Questionnaire 1	X						
Blood Draw		X	x				X
Phone/email/in-person to inform of potentially tolerated foods.				X			
Questionnaire 2				X			
Testing Foods Found as tolerable					X		
Questionnaire 3						X	
Questionnaire 4						X	X

172
173 B. Sources of Materials

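### The Aim 1 AUC does not separate foods by recent intake, although known triggers are kept out of the diet in the week before the draw and known safe foods are not

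*Combined protocol and SAP*

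**What the plan says.** **Diet before the draw.** Study Design step 6a states: "Only known 'safe foods' (foods that do not induce repetitive vomiting) are to be consumed" "for one week before blood draw". No reason for the rule is given.

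**Aim and analysis.** Specific aim 1 is: "Assess the assay's precision by its predictive accuracy in distinguishing safe foods from trigger foods". The Statistical Design paragraph models safe or trigger status with a random-effects logit on nine biomarkers and a subject effect, then computes a clustered ROC area with a 95% interval. The success rule reads: "The assay is predictive if the lower limit of the 95% CI is above 0.5, which is the null value indicating no" predictive ability. The paragraph has no term, stratum or restriction for recent intake. It does not say which foods enter the AUC, and it sets no separate criterion for new foods.

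**Where labels come from.** The inclusion criteria require triggers documented before entry: 2-3 in Group 1, 4 or more in Group 2. Foods introduced between the draw and the assay results go on Questionnaire Two, and the child's own clinicians choose them (step 8). Once results are known, "parents will be instructed to introduce new foods identified as potentially safe into" the diet (step 10b), with outcomes on Questionnaire Three. No analysis of either questionnaire is specified.

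**Later draw.** Step 12 and Sources of Materials describe a further draw, after several triggers are tolerated, that tests safe foods, triggers and outgrown triggers. It serves Aim 3.

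**The concern.** By rule, no known trigger is eaten in the run-in week, while some or all known safe foods are. Any food eaten that week is thus a known safe food, and every known trigger has gone at least a week without being eaten. The subject random effect does not deal with this, because the contrast lies between foods within a child.

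If a marker responded less to a food the child has just been eating, it would separate known safe foods from known triggers without carrying any information about disease. It would not help with a new food, and might place safe new foods alongside the triggers. Aim 1 could then declare the assay predictive on evidence that does not carry over to untried foods, which are its intended use. The bar is low (any AUC whose lower limit clears 0.5), so a modest shift could be enough.

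**Working it through.** The documents give no expected AUC, power or sample-size derivation, so there is no stated figure to reproduce.

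**Inputs from the plan.** Up to 20 children, up to 10 per group; 2-3 triggers, or 4 or more; trigger intake zero in the run-in week; success if AUC − 1.96 × SE > 0.5.

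**Assumptions.** f is the share of analysed safe foods eaten that week, and d is the shift in score (in residual SD) for a food that was eaten. Group 2 has 4-6 triggers, each child has 10 safe foods, child effect SD is 0.5 and residual SD is 1. The score carries no trigger signal. The documents give neither f nor d.

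**Step 1: a perfect intake detector.** Triggers are never eaten and a share f of safe foods is, so AUC = f × 1 + (1 − f) × 0.5 = 0.5 + f/2. For f = 0.25, 0.50, 0.75 and 1 this is 0.625, 0.75, 0.875 and 1.

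**Step 2: a noisy intake-only score.** For foods from different children (nearly all pairs), the difference in score has variance 2 × (1² + 0.5²) = 2.5, SD 1.581. At d = 0.5, an eaten safe food scores below a trigger with probability Φ(0.5/1.581) = Φ(0.316) = 0.624. Hence AUC ≈ 0.624f + 0.5(1 − f):

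- f = 0.2: 0.125 + 0.400 = 0.525
- f = 0.5: 0.312 + 0.250 = 0.562
- f = 0.8: 0.499 + 0.100 = 0.599

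**Step 3: how often the rule is met.** Simulated trials, Obuchowski clustered variance:

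| Share of safe foods eaten | d = 0 | d = 0.3 | d = 0.5 | d = 0.8 |
|---|---|---|---|---|
| 20% | about 3% | – | 10-14% | – |
| 50% | about 3% | about 20% | about 41% | about 75% |
| 80% | about 3% | about 40% | about 76% | about 99% |

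The nominal rate is 2.5%. Repeat runs agree within about 3 percentage points, except at 20% eaten, where one gave 14% and another 10%; both are shown as a range.

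**Step 4: dilution by new foods.** With 20 foods per child, f = 0.75 for known safe foods and d = 1, the rule is met in 98%, 73%, 30% and 3.2% of trials when new, uneaten foods make up 25%, 50%, 75% and 100% of the safe foods analysed.

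**Step 5: restriction to uneaten safe foods.** The same intake-only score then has AUC about 0.50 and meets the rule in about 3-4% of trials, whatever f and d.

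**Step 6: which new foods may be added.** Foods introduced under step 10b are there because their assay result looked safe. Take a score with no signal and no intake effect (d = 0), and let the selected foods come from the lower half of scores (an assumption). If 20%, 40% or 60% of the safe foods are selected in this way, the rule is met in about 24%, 65% or 92% of trials. Pooling these foods would replace one bias with another.

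**The case against.** The strongest reply is that the mechanism is hypothetical in three respects: that recent intake affects the assay at all, that the effect is specific to the food eaten, and that it runs in the safe direction. White cells are exposed to food homogenates for 3 hours outside the body, and the second hypothesis invokes innate immunity; neither points to a food-specific diet effect. All of this stands, which is why the figures above are conditional.

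A reader might infer that step 6a itself presumes recent intake changes the response to a food. The text does not support that. It gives no rationale, and the rule fits equally well with avoiding a recent reaction before sampling. Such an effect would be shared by all wells from one draw and would not separate foods within a child.

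A reader might also infer that the run-in creates the problem and should go. That does not follow. Families may avoid known triggers anyway, in which case step 6a only formalises an existing pattern and dropping it would not remove the confounding.

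Two further points hold in part. The later draw is a genuine partial check: hypothesis 2 expects outgrown triggers to keep their pattern while being eaten, whereas an intake-only score would lose it. That draw is outside the success rule, however. And if only foods new at the draw were to be analysed, this confounding would vanish, but the plan does not say so.

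Finally, Questionnaire One may record diet history; its content is not shown. The study grid places it at Day 0 and the draw at Day 0-14, so it cannot be relied on to cover the run-in week.

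**Conclusion.** The concern holds in a limited form. Among foods of known status, the trigger label is partly confounded with not having been eaten in the week before the draw, and nothing in the Aim 1 analysis or success rule addresses this. If a food-specific intake effect in the safe direction exists, an uninformative score could pass: roughly 10-14% to 76% of trials at 0.5 SD with 20% to 80% of safe foods eaten, against about 3% with no such effect. The rate falls as new foods enter the analysed set and returns to about 3% when all analysed safe foods are new.

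The documents do not show that the assay reads diet history, and it would be wrong to conclude that it does. What they do show is that the planned AUC could not tell the two explanations apart, and that the plan names no record of intake in that week from which to check afterwards.

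**What to change.** Leave the run-in and all diet instructions as they are, and make these changes:

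1. At the draw, record which foods were eaten in the preceding 7 days.
2. State which foods enter the Aim 1 AUC.
3. Pre-specify and report an AUC of triggers versus safe foods not eaten that week. The safe foods are known safe foods not currently eaten, plus foods introduced after the draw but before assay results are released (Questionnaire Two).
4. Require this AUC to support any claim about new foods, and report the AUC over all known foods alongside it.
5. Keep foods introduced under step 10b (Questionnaire Three) out of this AUC, because their scores are selected. Report their tolerance rate separately.

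The cost is a short food list at the draw and one added analysis. The restricted AUC will rest on fewer safe foods and have a wider interval, which matters with at most 20 children.

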174 The research material obtained from the human subjects

175 1. 6ml of blood in a K2 EDTA (lavender top) blood tube withdrawn by specialized phlebotomists in
176 the blood draw unit (0.5 ml of this will be used to isolate DNA for potential future sequencing under a
177 separate IRB). White blood cells (WBCs) will be isolated from 5.5 ml of blood using ACK buffer lysis of red
178 blood cells, within 1 hour of blood collection, as performed previously for the Case Study (HUM00155216).
179 Blood will be kept on ice in the K2 EDTA tubes during the waiting period (< 1 hour). WBCs will be plated in
180 24 well plates, and exposed to different food homogenates for 3 hours. Total RNA will be extracted, and RT-
181 qPCR for our gene panel will be used to generate the heatmap.

182 A second blood draw may be requested from a limited number of patients, at least 2-4 weeks after
183 the initial blood draw, for scRNA-seq. In this case, the blood will be prepared in the same manner as for the
184 initial draw above, but instead of extracting RNA, samples will be submitted to the UofM Advanced
185 Genomics Core for them to perform scRNA-seq on the samples. The data will be analyzed using the cloupe
186 software by 10x Genomics.

187 A third blood draw may occur (or second blood draw if scRNA were not performed for that patient)
188 after the patient recovers from several triggers. The patient will be screened at 3 month intervals, so the
189 third (or second if no scRNA-seq) will be performed for this purpose at least 3 months after the initial blood
190 draw. In this case, the cells will be prepared in the same manner as the initial blood draw, but treated with
191

193 only a limited number of safe, trigger foods, and outgrown trigger foods.

194 2. At the termination of the protocol samples and data will cease to be accessed, or otherwise
195 accessed again after IRB approval transferred to another existing protocol. There are no plans to destroy
196 records or samples.

197 **Protection of Information:**

198 All data will be kept on REDCap, a password-protected, HIPAA compliant, web-based application
199 developed by Vanderbilt University to capture data for clinical research and create databases and projects.
200 The databases use instruments such as surveys and forms as research capture tools. Projects are self-
201 sufficient and secure databases that can be used for normal data entry or for surveys across multiple

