202 distinct time points. Only study team members will have access to this data.

- 203 1. A master list that includes identifiable data will be kept in a REDCap "Study Housekeeping"
204 database that includes subject number, patient name, parent names, MRN, contact information
205 including address, email, phone number, documentation of blood draw, samples saved and filling
206 out of questionnaires.
- 207 2. All data variables will be kept in a separate "Research Data" REDCap database. Subjects will be
208 identified only by subject number in this database. Data will include:
- 209 a. Results of blood tests
210 b. Questionnaire answers
211 c. Age
212 d. Number of food reactions
213 e. Identified trigger foods
214 f. Identified tolerated foods.
- 215 3. Data downloaded for analysis will have only subject number included.
- 216 4. Stored RNA, DNA or cDNA samples will contain only the subject number without personal
217 identifiers.
- 218 5. Parents/guardians may request that stored blood samples be destroyed at the end of the study.

219 **C. Potential Risks**

220 **Describe potential risks**

221 The risk in this study arises due to incorrect predictions by the test. The current test being validated is not
222 an FDA-approved or cleared test. However, current standard of care recommends which foods to trial in a
223 random fashion, and incorrect predictions frequently occur leading to reactions. Hence this study will not
224 pose an added risk to the current standard of care. The indication of what to trial will be communicated to
225 the patients by the allergist and nutritionist as currently occurs in the standard of care. However, the only
226 difference is that the allergist and nutritionist will in this study use this assay for indication regarding what
227 foods to trial. If a food is falsely identified as safe by the assay but triggers a reaction, then these reactions
228 will be managed by the nutritionist and allergist as per current standard of care for failed trials.

229 Blood draw from infants and toddlers is a safe procedure with minimal risks. Trained and experienced
230 phlebotomists at UMHS perform blood draws on infants and toddlers routinely. The procedure may cause
231 anxiety for the infant/toddler. The test can result in a small bruise or mild soreness for the child at the site of
232 blood draw. The bruise can last for a few days.

233 A risk of breach of confidentiality always exists in all studies.

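### Nothing keeps each food's known status from the laboratory running the assay, so wells for documented trigger and safe foods can be repeated, excluded or normalised with the answer in view

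*Combined protocol and SAP*

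**What the plan says.** - **Who runs the test.** Section I.1.A, Study Design, step 9: "Blood will be analyzed by the PI in a research lab at the University of Michigan to determine" "differences in the PI's assay between potentially tolerated and not tolerated foods (see description of" a laboratory description at lines 216-232. Hypothesis 1 confirms that the team developed the test: "Our blood test that we developed will distinguish safe from trigger foods for FPIES patients".
- **What is known before the assay.** Both inclusion groups are defined by documented reactions to trigger foods. Exclusion criterion 3 removes "Patients who do not have at least 2 trigger foods identified". Step 6a limits the child to known safe foods for the week before the draw. So some triggers and some safe foods are known when the blood reaches the laboratory.
- **Where that information sits.** Under Protection of Information, the Research Data database holds blood test results, questionnaire answers, identified trigger foods and identified tolerated foods. On access the section says "Only study team members will have access to this data". Subject numbers hide the child's identity, not the status of a food.
- **How the readout is made.** Section I.1.B: RT-"qPCR for our gene panel will be used to generate the heatmap". No rule is given for repeating a well, excluding one, normalising the values or calling a food safe. The line reference in step 9 leads to text on sample storage and risks; the assay is described at lines 175-181.
- **Later draws.** For the third draw, foods are chosen by status: safe, trigger and outgrown trigger.
- **Success rule.** Statistical Design: a random-effects logit on 9 biomarkers, then a clustered AUC. The assay counts as predictive if the lower 95% limit is above 0.5.

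**The concern.** The stated objective is to validate a test. In an accuracy study, the index test should be processed without sight of the reference status, because discretionary steps otherwise tend to run towards agreement.

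RT-qPCR values are instrument readings, so the discretion lies around them: which wells to rerun, which to drop, how to normalise. An odd-looking value for a known trigger invites a rerun; the same value for a food of unknown status would not. If reruns depend on both the value and the known status, the AUC rises even when the assay carries no information.

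Much of the trigger class appears to be exposed. Under step 10b the foods introduced on the assay's advice are those identified as potentially safe. New triggers can therefore enter mainly through wrong safe calls, or through foods introduced before the results are released. Most trigger foods in the ROC analysis would then be those documented before entry. At stake are the study's only success criterion and, through the third draw, Aim 3 on persistence of the reaction.

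**Working it through.** The plan gives no expected AUC, power or number of known-status foods per child, so there is no figure of its own to reproduce. The following illustrates vulnerability only.

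**Inputs**
- Children: 20, the maximum planned (10 per group).
- Triggers per child: 2 in ten children and 4 in ten, the group minimums. Trigger wells: 10 × 2 + 10 × 4 = 60.
- Foods per child: 20, *assumed*. The Background says the assay screens more than 20 foods, but not how many have known status. Safe wells: 20 × 20 − 60 = 340.
- *Assumed*: one score per food, independent foods, true AUC 0.5, Hanley-McNeil standard error.

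**Step 1. The AUC needed to pass.** With a = A/(2 − A) and b = 2A²/(1 + A),

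SE² = [A(1 − A) + (n₁ − 1)(a − A²) + (n₂ − 1)(b − A²)] / (n₁n₂).

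At A = 0.581, n₁ = 60, n₂ = 340: a = 0.4094, b = 0.4270, A² = 0.3376.

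SE² = [0.243 + 59 × 0.0719 + 339 × 0.0895] / 20,400 ≈ 34.8 / 20,400 ≈ 0.00171, so SE ≈ 0.0413.

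Lower limit = 0.581 − 1.96 × 0.0413 ≈ 0.500.

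An observed AUC of about 0.58 is therefore enough. On a normal scale that is a shift of √2 × Φ⁻¹(0.581) ≈ 0.29 SD between trigger and safe wells. With a design effect of 2 for clustering, the bar rises to an AUC of about 0.61, or 0.41 SD.

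**Step 2. What selective repeats do to a worthless assay.** In each child the trigger well that looks least like a trigger is rerun and the new value kept. That touches 20 of 400 wells (5%), or 20 of 60 trigger wells (one third).

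| Well handling | Mean AUC | Success rule met |
|---|---|---|
| No repeats | 0.50 | about 2.4% |
| Most discordant trigger well per child repeated | about 0.58 | about 47% to 49% across separate runs |
| Most discordant trigger and most discordant safe well per child repeated | about 0.61 | about 74% |

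The middle row fits step 1: the mean AUC sits almost on the passing threshold, so about half of the studies pass.

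**Step 3. What drives it.** Repeating wells is harmless in itself. A well rerun without regard to its status and value gets a fresh draw from the same distribution, and the AUC stays at 0.50. The bias needs status and value to be seen together, and that is what coding removes.

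**The case against.** The case against is substantial and narrows the point.

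- **The endpoint has no cut.** A reader might infer that the analyst could choose a threshold for each child with status in view. On a null assay with 20 foods and 3 triggers, that gives an average Youden index of about 0.33. But the plan reports a model-based AUC and describes no per-child cut, and with one cut pooled over all children the index falls to about 0.07 to 0.08. That route does not measure this study's endpoint.
- **Who makes the safe call is not stated.** A reader might infer that the PI does. Step 10 is in the passive voice. Step 9 and the hand-over to the clinical team point to the PI's laboratory, but this is inference.
- **The contents of Questionnaire One are not described.** The plan says "Parent/Guardian will be asked to fill out Questionnaire One at the time of entry into the study", and a reader might infer that it records food status. The point does not need this, because eligibility already fixes the triggers.
- **New foods are protected.** Foods introduced after the call have no known status when the assay is read, and Questionnaire Two is requested back only when results are communicated. The exposure does not extend to these foods.
- **No misconduct is shown.** The plan describes no selective repeats and does not say that the laboratory receives trigger lists.

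All of this stands. What remains is that status is available to the study team, nothing excludes the person running the assay, and no rule governs the wells.

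**Conclusion.** The concern holds for foods whose status is known when the assay is run. The documents give the assay to its owner, make trigger status available beforehand, and provide neither masking nor rules for handling wells. They do not support a claim that all readings can be fitted to the answer, or that the PI is known to make the safe calls.

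In the illustration, one status-guided repeat per child raises a worthless assay's chance of success from about 2.4% to just under half. This rests on 20 children, 20 independent foods each, the minimum trigger counts and a Hanley-McNeil interval. More triggers per child would dilute the effect of one repeat, and an interval widened for clustering would raise the bar. It shows what the plan leaves open, not what would happen.

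The plan should be changed before samples are run, because unmasked processing cannot be repaired afterwards. Masking would not cure a separate problem: scoring the 9-biomarker model on the data used to fit it.

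**What to change.** 1. In step 9, have the existing study coordinator, provided that person works outside the laboratory, select the foods and assign coded labels. Withhold trigger and safe lists from the laboratory, and restrict its access to those fields in the Research Data database.
2. Before the first sample, write down the rules for repeating, excluding and normalising wells, to be applied without reference to food status.
3. Lock the expression values and any safe/trigger calls in the Research Data database before they are linked to food status.
4. For the third draw, where foods are chosen by status, have the coordinator make the selection and supply only coded labels.
5. Report the AUC separately for known-status foods and for foods introduced after the call.

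**Cost.** A coding sheet, a locked upload, a small coordination burden and a short delay before results are released; no extra blood. Some homogenates may be recognisable as foods, but that does not reveal whether the food is that child's trigger. The separate AUC for later foods may be imprecise, since few of them are likely to prove triggers.
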